### **3.7. Visit Windows**

#### **3.7.1. Definition of Predose, Postdose, Study Day**

Predose value is defined as the last available value off-treatment collected prior to study drug administration.

Postdose value is defined as any value collected after the study drug administration and before the dosing date plus 30 days.

Study Day will be calculated from the date of GS-9876 administration and derived as follows:

- For postdose study days: assessment date – dosing date + 1
- For days prior to the dose: assessment date – dosing date

Therefore, study day 1 is the day of study drug administration.

### 3.7.2. Analysis Windows

The nominal visit as recorded on the CRF will be used when data are summarized by visit. Any data relating to unscheduled visits will not be assigned to a particular visit or time point and in general will not be included in summaries. However, the following exceptions will be made:

- An unscheduled visit prior to the first dose of study drug may be included in the calculation of predose value, if applicable.
- For subjects who prematurely discontinue from the study, ET data will be summarized as a separate visit, labeled ‘Early Termination’.

The predose and postdose visits for vital signs for different cohorts are summarized in [Table 3-1](#).

**Table 3-1. Predose and Postdose Visits of Vital Signs**

Visit Label	Study Day and Time points
Predose	1 (predose)
Day 1	1 (1, 3, 6, and 12 hours postdose)
Day 2	2
Day 3	3
Day 4	4
Day 5	5
Day 6	6
Follow-up	15 ( $\pm 1$ )
Early Termination	Early Termination (if applicable)

The predose and postdose visits for laboratory tests for different cohorts are summarized in [Table 3-2](#).

**Table 3-2. Predose and Postdose Visits of Laboratory Tests**

Visit Label	Study Day and Time points
Predose	-1
Day 1	1 (4 hours postdose)
Day 2	2 (chemistry and urinalysis only)
Day 3	3
Day 6	6
Follow-up	15 ( $\pm 1$ )
Early Termination	Early Termination (if applicable)

The predose and postdose visits for ECG for different cohorts are summarized in [Table 3-3](#).

**Table 3-3. Predose and Postdose Visits for Electrocardiogram**

Visit Label	Study Day and Time points
Predose	-1
Day 1	1
Day 6	6
Follow-up	15 ( $\pm 1$ )
Early Termination	Early Termination (if applicable)

### 3.7.3. Selection of Data in the Event of Multiple Records on the Same Day

Depending on the statistical analysis method, single values may be required for each day. For example, change from predose by visit usually requires a single value.

If multiple, valid, nonmissing numeric observations exist on a day, records will be chosen based on the following rules if a single value is needed:

- For predose, the last available record on or prior to the date and time of the first dose of study drug will be selected. If there are multiple records with the same time or no time recorded on the same day, average (arithmetic or geometric mean, as appropriate) will be used for the predose value.
- For postdose visits:
  - The record closest to the nominal day for that visit will be selected.
  - If there are 2 records that are equidistant from the nominal day, the later record will be selected.
  - If there is more than 1 record on the selected day, the average will be taken, unless otherwise specified.

If multiple, valid, nonmissing categorical observations exist on a day, records will be chosen based on the following rules if a single value is needed:

- For predose, the last available record on or prior to the date and time of the first dose of study drug will be selected. If there are multiple records with the same time or no time recorded on the same day, the value with the lowest severity will be selected (eg, normal will be selected over abnormal for safety ECG findings).

- For postdose visits, if there are multiple records with the same time or no time recorded on the same day, the most conservative value within the window will be selected (eg, abnormal will be selected over normal for safety ECG findings).

## **4. SUBJECT DISPOSITION**

### **4.1. Subject Enrollment and Disposition**

A summary of subject enrollment and disposition will be provided by renal function group and by renal function group within each cohort. The number and percentage of subjects in each of the categories listed below will be provided. The denominator for the percentage calculation will be the total number of subjects in the renal function groups included in the All Enrolled Analysis Set.

- Safety Analysis Set
- PK Analysis Set
- Completed study drug
- Did not complete study drug with reasons for study drug discontinuation, as applicable
- Completed study
- Did not complete study with reasons for study discontinuation, as applicable

In addition, the total number of subjects who were enrolled, and the number of subjects in each of the disposition categories listed above will be displayed in a flowchart.

The following by-subject listings will be provided by subject ID number in ascending order to support the above summary tables:

- Reasons for premature study drug or study discontinuation

A by-subject listing of subject disposition including renal function group, date of study drug administration (study days), study drug completion status, reason for study drug discontinuation (if applicable), study completion status, reason for study discontinuation (if applicable) will be provided by subject ID number in ascending order.

For a control subject may be matched to multiple renal impaired subjects across different cohorts, a by-subject listing of subject match and cohort affiliation will be provided.

### **4.2. Extent of Exposure**

A subject's extent of exposure to study drug data will be generated from the study drug administration page in the eCRF. Study drug administration data for subjects who received study drug will be listed.

A listing for subjects who were enrolled but not dosed will also be provided.

#### **4.3. Protocol Deviations for Eligibility**

A by-subject listing will be provided for the enrolled subject who failed to meet all inclusion criteria or met at least 1 exclusion criterion. The listing will present the eligibility criterion (or criteria if more than 1 violation) that subjects did not meet and related comments, if collected.

Protocol deviations occurring after subjects entered the study are documented during routine monitoring. Any deviations identified will be evaluated to determine if it justifies excluding the subject from any analysis sets.

#### **4.4. Important Protocol Deviations**

A by-subject listing will be provided for those subjects who had important protocol deviations.

## 5. BASELINE CHARACTERISTICS

### 5.1. Demographics

Subject demographic variables (ie, age, sex, race, and ethnicity) will be summarized by renal function group and overall using descriptive statistics for age, and using number and percentage of subjects for sex, race, and ethnicity. The summary of demographic data will be provided for the Safety Analysis Set.

A by-subject demographic listing, including the informed consent date, will be provided by subject ID number in ascending order.

### 5.2. Baseline Characteristics

Baseline characteristics include body weight (in kg), height (in cm), and body mass index (BMI; in kg/m^2), CLcr (mL/min) using Cockcroft-Gault formula, and estimated glomerular filtration rate (eGFR) using the Modification of Diet in Renal Disease (MDRD) Study equation {[National Institute of Diabetes and Digestive and Kidney Diseases \(NIH\) 2016](#)}. The equation used for MDRD-based eGFR is as follows:

$$\text{eGFR (mL/min/1.73m}^2\text{)} = 175 \times (\text{S}_{\text{cr}})^{-1.154} \times (\text{Age})^{-0.203} \times (0.742 \text{ if female}) \times (1.212 \text{ if African American}),$$

where  $\text{S}_{\text{cr}}$  is serum creatinine in mg/dL.

These baseline characteristics will be summarized by renal function group (determined based on CLcr value from Cockcroft-Gault formula) using descriptive statistics (numbers of subjects, mean, SD, median, Q1, Q3, minimum, and maximum) for continuous variables and using the numbers and percentages of subjects for categorical variables. For baseline body weight, height, BMI, CLcr and eGFR, descriptive statistics also will be presented by sex in the same table. The summary of baseline characteristics will be provided for the Safety Analysis Set. No formal statistical testing is planned.

A by-subject listing of other baseline characteristics will be provided by subject ID number in ascending order.

### 5.3. Medical History

Medical history data will be collected at screening and listed only. General medical history data will not be coded.

A by-subject listing of general medical history will be provided by subject ID number in ascending order. The listing will include relevant medical condition or procedure reported term, onset date, ongoing status, and resolution date (if applicable).

## **6. EFFICACY ANALYSES**

Efficacy will not be evaluated in the study.

## **7. SAFETY ANALYSES**

### **7.1. Adverse Events and Deaths**

#### **7.1.1. Adverse Event Dictionary**

Clinical and laboratory AEs will be coded using the current version of the Medical Dictionary for Regulatory Activities (MedDRA). System organ class (SOC), high-level group term, high-level term, preferred term (PT), and lower-level term will be provided in the AE dataset.

#### **7.1.2. Adverse Event Severity**

Adverse events are graded by the investigator as Grade 1, 2, 3, 4 or 5 according to toxicity criteria specified in the protocol. The severity grade of events for which the investigator did not record severity will be categorized as “missing” for tabular summaries and data listings. The missing category will be listed last in summary presentation.

#### **7.1.3. Relationship of Adverse Events to Study Drug**

Study drug related AEs are those for which the investigator selected “Related” on the AE CRF to the question of “Related to Study Treatment”. Relatedness will always default to the investigator’s choice, not that of the medical monitor. Events for which the investigator did not record relationships to study drug will be considered related to study drug for summary purposes. However, by-subject data listings will show the relationship as missing from that captured on the CRF.

#### **7.1.4. Relationship of Adverse Events to Study Procedure**

Study procedure related AEs are those for which the investigator selected “Related” on the AE CRF to the question of “Related to Study Procedures”. Relatedness will always default to the investigator’s choice, not that of the medical monitor. Events for which the investigator did not record relationships to study procedures will be considered related to study procedures for summary purposes. However, by-subject data listings will show the relationship as missing from that captured on the CRF.

#### **7.1.5. Serious Adverse Events**

Serious adverse events (SAEs) will be identified and captured as SAEs if AEs met the definitions of SAE specified in the study protocol. Serious adverse events captured and stored in the clinical database will be reconciled with the SAE database from the Gilead pharmacovigilance department before database finalization.

## **7.1.6. Treatment-Emergent Adverse Events**

### **7.1.6.1. Definition of Treatment Emergent**

Treatment-emergent adverse events (TEAEs) are defined as 1 or both of the following:

- Any AEs with an onset date on or after the study drug start date and no later than 30 days after permanent discontinuation of study drug. If the AE onset date is the same as the date of study drug start date then the AE onset time must be on or after the study drug start time. If the AE onset time is missing when the start dates are the same the AE will be considered treatment emergent.
- Any AEs leading to premature discontinuation of study drug.

### **7.1.6.2. Incomplete Dates**

If the onset date of the AE is incomplete and the AE stop date is not prior to the first dosing date of study drug, then the month and year (or year alone if month is not recorded) of onset determine whether an AE is treatment emergent. The event is considered treatment emergent if both of the following 2 criteria are met:

- The AE onset is the same as or after the month and year (or year) of the date of first dose of study drug, and
- The AE onset date is the same as or before the month and year (or year) of the date corresponding to 30 days after the date of the last dose of study drug

An AE with completely missing onset and stop dates, or with the onset date missing and a stop date later than the date of the first dose of study drug, will be considered to be treatment emergent. In addition, an AE with the onset date missing and incomplete stop date with the same or later month and year (or year alone if month is not recorded) as the first dosing date of study drug will be considered treatment emergent.

## **7.1.7. Summaries of Adverse Events and Deaths**

Treatment-emergent AEs will be summarized based on the Safety Analysis Set.

The number and percentage of subjects who experienced at least 1 TEAE will be provided and summarized by SOC, PT, and renal function group based on the Safety Analysis Set as follows:

- All TEAEs
- All TEAEs by SOC and PT
- All TEAEs by severity
- All treatment-related AEs

- All TEAEs of Grade 2 or higher
- All treatment-related AEs by severity
- All treatment-emergent SAEs
- All treatment-related SAEs
- All TEAEs leading to study discontinuation

A brief, high-level summary of AEs described above will be provided by renal function group and by the number and percentage of subjects who experienced the above AEs. All deaths observed in the study will also be included in this summary.

Multiple events will be counted only once per subject in each summary. Adverse events will be summarized and listed first in alphabetic order of SOC and then by PT in descending order of total frequency within each SOC. For summaries by severity, the most severe grade will be used for those AEs that occurred more than once in an individual subject per treatment during the study.

In addition, data listings will be provided for the following:

- All AEs (indicating whether the event is treatment emergent)
- All SAEs
- Deaths

#### **7.1.8. Additional Analysis of Adverse Events**

No additional analysis of AEs is planned.

#### **7.2. Laboratory Evaluations**

Laboratory data collected during the study will be analyzed and summarized using both quantitative and qualitative methods. Summaries of laboratory data will be provided for the Safety Analysis Set and will include data collected up to the last dose of study drug plus 30 days for subjects who have permanently discontinued study drug. The analysis will be based on values reported in conventional units. When values are BLQ, they will be listed as such, and the imputed value will be used for the purpose of calculating summary statistics. Hemolyzed test results will not be included in the analysis, but they will be listed in by-subject laboratory listings.

A by-subject listing for laboratory test results will be provided by subject ID number and time point in chronological order for hematology, chemistry, and urinalysis separately. Values falling outside of the relevant reference range and/or having a severity grade of 1 or higher on the protocol specified severity grading will be flagged in the data listings, as appropriate.

No inferential statistical testing is planned for laboratory assessments.

### **7.2.1. Summaries of Numeric Laboratory Results**

Descriptive statistics will be provided by renal function group for each laboratory test as follows:

- Predose values
- Values at each postdose time point
- Change from predose at each postdose time point

Predose and postdose values will be defined as described in Section 3.7.1. Change from predose to a postdose visit will be defined as the visit value minus the predose value. The mean, median, Q1, Q3, minimum, and maximum values will be displayed to the reported number of digits; SD values will be displayed to the reported number of digits plus 1.

In the case of multiple values in an analysis window, data will be selected for analysis as described in Section 3.7.3.

### **7.2.2. Graded Laboratory Values**

The Common Toxicity Criteria for Adverse Events (CTCAE) Version 4.03 will be used to assign toxicity grades to laboratory results for analysis. Grade 0 includes all values that do not meet the criteria for an abnormality of at least Grade 1. For laboratory tests with criteria for both increased and decreased levels, analyses for each direction (ie, increased, decreased) will be presented separately.

#### **7.2.2.1. Treatment-Emergent Laboratory Abnormalities**

Treatment-emergent laboratory abnormalities are defined as values that increase at least 1 toxicity grade from predose assessment at any postdose time point, up to and including the date of last dose of study drug plus 30 days for subjects who permanently discontinued study drug. If the relevant predose laboratory value is missing, any abnormality of at least Grade 1 observed within the time frame specified above will be considered treatment emergent.

#### **7.2.2.2. Summaries of Laboratory Abnormalities**

Laboratory data that are categorical will be summarized using the number and percentage of subjects in the study with the given response at predose and each scheduled postdose time point.

The following summaries (number and percentage of subjects) for treatment-emergent laboratory abnormalities will be provided by laboratory test and renal function group; subjects will be categorized according to the most severe postdose abnormality grade for a given laboratory test:

- Treatment-emergent Graded laboratory abnormalities

- Treatment-emergent Grade 3 or higher laboratory abnormalities

For all summaries of laboratory abnormalities, the denominator is the number of subjects with nonmissing postdose values up to 30 days after last dosing date.

A by-subject listing of treatment-emergent laboratory abnormalities will be provided by subject ID number and time point in chronological order. This listing will include all test results that were collected throughout the study for the lab test of interest, with all applicable severity grades displayed.

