1.5. Risk/Benefit Assessment for the Study

While there is no direct benefit for the subject participating in the renal impairment study of GS-9876, the risks are considered to be minimal for the following reasons:

GS-9876 has been in a battery of nonclinical animal studies, and no renal toxicity was identified.

GS-9876 has been tested in humans as a single ascending dose over a dose range of 2 to 50 mg (GS-US-379-1372) and as a multiple ascending dose over a dose range of 15 to 50 mg (GS-US-379-1900) and no evidence of nephrotoxicity has been observed. In general GS-9876 was well tolerated at all dose levels. The planned single dose of 20 mg of GS-9876 is well below the highest dose given in the healthy volunteers and is expected to be tolerated well.

As discussed in Section 1.3, the disposition of GS-9876 is primarily via hepatic metabolism and elimination with minimal excretion expected in urine and the impact on renal impairment on GS-9876 PK is expected to be limited. Subjects in this study will receive a single 20 mg dose of GS-9876, which is expected to provide a margin of 2.8-fold to the NOAEL exposure in the 39-week Cynomolgus monkey toxicology study.

Evidence of deterioration in kidney function in humans can readily be detected and monitored using routine laboratory tests. For this study, frequent assessments of kidney function will be performed from the collection of both blood and urine samples. While subjects with renal impairment will be enrolled, the risk of further kidney injury in these subjects should be minimized by this close renal monitoring. Further, this study will enroll subjects with moderate renal impairment (Cohort 1) with a screening estimated creatinine clearance (CL_{cr}) of 30-59 mL/min first. Data from these subjects will be compared to matched subjects with normal renal function ($CL_{cr} \geq 90$ mL/min). Subjects with severe renal impairment (Cohort 2; CL_{cr} 15-29 mL/min) will only be evaluated if supported by safety and/or PK data from Cohort 1.

There are several potential causes of nephropathy in patients with chronic autoimmune diseases: primary autoimmune attack on the kidney, secondary renal amyloidosis, drug-related renal disease due to necessary drugs used to treat the primary autoimmune disease. Kidney disease and

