8.6.3. Laboratory Evaluations

Listings of individual subject laboratory results will be provided. Laboratory results and change from predose values for selected lab tests will be summarized by renal function group at scheduled visits. The incidence of treatment-emergent graded laboratory abnormalities will be summarized by treatment.

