### **7.5. Electrocardiogram Results**

#### **7.5.1. Investigator Electrocardiogram Assessment**

A shift table of the investigator's assessment of ECG results at each scheduled visit compared with predose values will be presented by renal function group using the following categories:

normal; abnormal, not clinically significant; abnormal, clinically significant; or missing. The number and percentage of subjects in each cross-classification group of the shift table will be presented. Subjects with a missing value at predose or postdose will not be included in the denominator for percentage calculation. No formal statistical testing is planned.

A by-subject listing for ECG assessment results will be provided by subject ID number and time point in chronological order.

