#### **7.7. Changes From Protocol-Specified Safety Analyses**

There are no changes from the protocol-specified safety analyses.

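### The SAP's summary of categorical laboratory results names no renal function group and makes no within-subject comparison with predose, so worsening in ungraded urinalysis results can be offset by improvement in other subjects

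*SAP*

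**What the plan says.** For categorical laboratory data, SAP 7.2.2.2 has one rule: "Laboratory data that are categorical will be summarized using the number and percentage of subjects in the study with the given response at predose", with the same count at each scheduled postdose time point. It gives no grouping variable, change or shift.

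The neighbouring rules are more specific:

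- The next rule in SAP 7.2.2.2, on treatment-emergent graded abnormalities, says its tables "will be provided by laboratory test and renal function group". SAP 7.2.2.1 defines these abnormalities as "values that increase at least 1 toxicity grade from predose assessment at any postdose time point".
- Numeric laboratory results (SAP 7.2.1) and vital signs (SAP 7.3) are given by renal function group, with change from predose.
- ECG assessments, which are also categorical, get a shift table (SAP 7.5.1) in which each visit's result "compared with predose values will be presented by renal function group".

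Protocol 8.6 asks for safety data collected from dosing onward to be summarized by renal function group. Protocol 8.6.3 adds: "Laboratory results and change from predose values for selected lab tests will be summarized by renal function group at scheduled visits". SAP 7.7 declares: "There are no changes from the protocol-specified safety analyses".

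**The concern.** The sentence describes the counted population as subjects in the study, while the rules around it specify renal function group. A programmer working from the SAP alone could produce a single column for everyone. The secondary objective is safety in subjects with normal and with impaired renal function, and one column cannot describe the two separately.

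The form of the table is a separate matter. Counts at each visit show how many subjects have a finding on that day, but not who acquired it since predose. Impaired subjects may well have abnormal urine findings before dosing (an assumption; the documents give no rates), so the useful question is whether a subject's result worsened.

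Urine results carry some weight here. Protocol 1.5 supports its risk assessment by saying that "frequent assessments of kidney function will be performed from the collection of both blood and urine samples", and urinalysis is scheduled at Screening, on Days -1, 1, 2, 3 and 6, and at follow-up.

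**Working it through.** The plan gives no figure for urinalysis findings, so there is none to reproduce. The check has a textual part and an arithmetical part.

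**Grouping.** The SAP sentence is silent on renal function group. Protocol 8.6 sets the general rule and Protocol 8.6.3 repeats it for laboratory results, and SAP 2.4 and 7.7 declare no departure. Read together, the documents require grouping, and the SAP sentence fails to say so.

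**Comparison with predose.** Protocol 8.6.3 limits change from predose to selected tests. SAP 7.2.1 defines change as a subtraction, which suits numeric results. The graded tables compare with predose, but only for tests that carry a grade. No summary does this for ungraded categorical results.

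**Denominator.** SAP 7.2.2.2 closes with: "For all summaries of laboratory abnormalities, the denominator is the number of subjects with nonmissing postdose values up to 30 days after last dosing date". This denominator is defined by postdose data and does not fit a predose row.

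**Size of the cancellation.** Inputs: 10 subjects per group (Protocol 3.1, Cohort 1). Assumed: 5 of 10 impaired and 0 of 10 control subjects positive at predose. Let *w* impaired subjects turn positive and *i* turn negative, with *n* = 10.

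- Change shown in a grouped table = (*w* − *i*)/*n*
- Share of the group that worsened = *w*/*n*
- Shortfall = *i*/*n*

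With *w* = 3, the share that worsened is 3/10 = 30% throughout:

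| Improvers *i* | Impaired positive after dosing | Change shown, grouped | Shortfall |
|---|---|---|---|
| 0 | 8/10 = 80% | +30 points | 0 |
| 1 | 7/10 = 70% | +20 points | 10 points |
| 2 | 6/10 = 60% | +10 points | 20 points |
| 3 | 5/10 = 50% | 0 | 30 points |

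The shortfall depends only on how many improve. It is zero if nobody does.

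**Dilution, only if the sentence were programmed as one column.** With *w* = 3 and *i* = 0, the impaired group goes from 5/10 to 8/10 (+30 points), and the 20 subjects together go from 5/20 = 25% to 8/20 = 40% (+15 points). More generally, *k* events confined to one group of 10 give *k*/10 by group, *k*/20 in Cohort 1 and *k*/60 at maximum enrolment. For *k* = 3 these are 30%, 15% and 5%, a dilution by a factor of 2 and of 6.

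**The case against.** **A reader might infer that the SAP pools the renal groups.** The documents do not support this. The sentence never says that groups are combined, and the protocol requires grouping with no departure declared. The dilution figures therefore describe a programming risk, not the plan.

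**A reader might infer that the SAP breaks a protocol promise on change from predose.** Protocol 8.6.3 makes that promise for selected tests only, and nothing in either document promises a shift table for categorical laboratory data. The ECG table shows that a better display is available, but its absence here is not in itself an error.

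**A reader might infer that worsening urine findings would go unseen.** That goes too far. SAP 7.2 plans a separate chronological urinalysis listing by subject, with out-of-range or graded values flagged as appropriate. At about 10 subjects per group it can be read directly. Laboratory abnormalities that need intervention are recorded as adverse events (Protocol 7.1.3), which SAP 7.1.7 summarizes by renal function group. For any graded urinalysis item, a subject whose grade rises is counted against predose by group, and an improver cannot cancel that count. The documents only link to the CTCAE text, so they do not settle which urinalysis items are graded.

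The SAP sentence also does not mention urinalysis; that it is the main categorical laboratory data is an inference. All the counts above are assumed.

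Most of this stands and limits the point. It does not remove the missing group name, the ill-fitting denominator, or the lack of a within-subject summary for ungraded categorical results. A listing lets a reader rebuild the shifts by hand, but it does not summarize them.

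**Conclusion.** The point holds as a minor one. The SAP sentence should name renal function group, as the protocol requires. Even when grouped, its visit counts can understate worsening in ungraded categorical results by the share of subjects who improve: 0 to 30 points in the illustration with 3 of 10 worsening. This rests on three assumptions: urinalysis is the main categorical laboratory data, at least some of its items carry no toxicity grade, and some subjects improve while others worsen. Safety here is a secondary, descriptive objective, and the primary pharmacokinetic comparison is not affected.

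**What to change.** Revise the sentence in SAP 7.2.2.2 along these lines:

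> Categorical laboratory results will be presented for each renal function group, as the number and percentage with each response at predose and at each scheduled postdose visit. Percentages are based on subjects with a nonmissing result at that visit. For urinalysis results that carry no toxicity grade, a shift table of predose against worst postdose result will be given by renal function group.

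The SAP should also state which urinalysis items are graded and, for the others, which direction counts as worse. The handling of missing results can follow the ECG shift table in SAP 7.5.1. Shifts to each visit can be added if wanted; the shift to the worst postdose result matters most, because it also collects subjects who turn at different visits.

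The cost is a wording change and a few extra descriptive tables, covering up to four renal function groups. They use data already collected, and no study procedure changes.
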